9.0 SAMPLE SIZE

The primary objective of this study is to determine whether Total Laparoscopic (TLRH) or Robotic Radical Hysterectomy (TRRH) is equivalent to Total Abdominal Radical Hysterectomy (TARH) with respect to 4.5 year disease free survival. If the disease free survival does not differ by more than 7% then the two procedures will be considered to be equivalent.

The 4.5 year disease free survival rate for patients undergoing TARH is estimated to be 90%. The following table, based on exponential survival times, gives the sample sizes required for levels of differences in disease free survival rates at 4.5 years. These differences will be regarded as being equivalent based on different accrual and follow-up times. The sample sizes assume a power of 80%, 95% confidence and two-tailed comparisons.

Based on these numbers, for a 4.5-year accrual and 4.5-year follow-up, a total of 740 patients (370 per arm) would be sufficient to declare equivalence with an equivalence margin of 7.2% or less at 4.5 years. If accrual is sufficiently rapid (ie less than 4.5 years), consideration will be given to increasing the sample size to reduce the amount of follow-up required but maintain the equivalence margin. This sample size will have 87% power to detect a non-inferiority margin of the same magnitude.

Table for Option 1 Randomised Design

| 4yr Disease Free Survival difference to be regarded as equivalent | | Years | Total Sample Size | |
|-------------------------------------------------------------------|------|---------|-------------------|------|
| TLRH/TRRH | TARH | Accrual | Follow-up | |
| | | 3 | 3 | 1660 |
| | | 3 | 4 | 1380 |
| 85 | 90 | 3 | 5 | 1190 |
| | | 4 | 4 | 1280 |
| | | 4 | 5 | 1114 |
| | 90 | 3 | 3 | 750 |
| | | 3 | 4 | 760 |
| 84 | | 3 | 5 | 654 |
| 04 | | 4.5 | 4.5 | 740 |
| | | 4 | 5 | 614 |
| | | 5 | 4 | 656 |
| | | 3 | 3 | 794 |
| | | 3 | 4 | 660 |
| 85 | 92 | 3 | 5 56 | |
| | | 4 | 4 | 612 |
| | | 4 | 5 | 532 |

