5.0 STUDY DESIGN

This Phase III international, multi-centre, open-label, randomized clinical trial design is an equivalence study with the hypothesis that TARH is equivalent TLRH in terms of disease free survival (DFS). The study will be conducted in two stages.

5.1 STAGE 1

The first stage will assess feasibility of recruitment and delivery of the intervention and collect quality of life on the first 100 patients.

5.2 STAGE 2

The Trial Management Committee (refer to Section 19.2) will decide whether the trial will progress along Option 1 or Option 2 based on clinical and economical feasibility and the level of interest amongst the clinical community.

[figure not shown]
Option 1

A randomized equivalence trial with disease-free survival as the endpoint is the definitive means of determining whether TLRH is at least equivalent to TARH. As such, it is planned to extend the trial to a larger randomized equivalence clinical trial (additional 640 patients) assessing disease free survival at 4.5 years from surgery.

Option 2

The study will follow-up the cohort of patients who had received a total laparoscopic or robotic radical hysterectomy for a minimum of 4.5 years post-surgery to determine whether the estimate of disease-free survival for patients who undergo laparoscopic or robotic surgery is consistent with the (control group) four-year disease-free survival rate of 90%.

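### The 90% control disease-free survival is a 4.5-year rate in the section 9.0 text but a 4-year rate in section 5.2, the table header and most of the table's arithmetic, and the stated 80% and 87% powers do not match each other

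*Protocol*

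**What the plan says.** The section 9.0 text places the control rate at the time point of the primary outcome: "The 4.5 year disease free survival rate for patients undergoing TARH is estimated to be 90" per cent. It introduces the table with "The following table, based on exponential survival times" and says that it "gives the sample sizes required for levels of differences in disease free survival rates at 4.5 years". The error rates are given as "The sample sizes assume a power of 80%, 95% confidence and two-tailed comparisons".

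The header of that table reads "4yr Disease Free Survival difference to be regarded as equivalent". Section 5.2, under Option 2, asks whether survival after laparoscopic or robotic surgery is "consistent with the (control group) four-year disease-free survival rate of 90" per cent.

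For the chosen design (4.5 years of accrual, 4.5 years of follow-up), section 9.0 says "a total of 740 patients (370 per arm) would be sufficient to declare equivalence with an equivalence margin of 7.2% or less at 4.5 years". The opening paragraph of the same section gives the margin as 7%. The section then adds "This sample size will have 87% power to detect a non-inferiority margin of the same magnitude".

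**The concern.** The control rate and its time point together fix the hazard and the variance in this calculation. Under the plan's own exponential model, 90% at 4 years and 90% at 4.5 years are different control arms, because the first implies 0.9^(4.5/4) = 88.8% at 4.5 years. The primary outcome (section 7.1) is disease-free survival at 4.5 years, so a table computed at 4 years does not answer the question that the text puts to it.

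Two uses depend on this. Section 9.0 allows the sponsor to enlarge the sample in exchange for shorter follow-up at the same margin, and this table is the only basis shown for that trade. Option 2 in section 5.2 follows patients for at least 4.5 years but judges them against a benchmark labelled as four-year.

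The two stated powers raise a second question, since they are given for the same sample size and the same size of margin.

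**Working it through.** **Inputs.** From section 9.0: 1:1 allocation, exponential survival, 95% confidence (2.5% per side), 80% power, N = 740 (370 per arm), margin 7.2% (7% in the opening paragraph), accrual A and follow-up F as listed. Assumed here: uniform accrual, no losses, true difference zero. For 80% equivalence power each side needs 90%, so z = 1.96 + 1.2816 = 3.2415 and z² = 10.507.

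**Step 1: reproduce the table.** With hazard l = −ln(S)/T, where T is the time at which S is read, and event probability P = 1 − (e^(−lF) − e^(−l(A+F)))/(lA):

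N = 2z² [l1²/P1 + l2²/P2] / (l1 − l2)²

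Example, 90 v 85, A = 3, F = 3, T = 4: l1 = 0.02634, l2 = 0.04063, P1 = 0.1115, P2 = 0.1666, giving N = 1660. The printed value is 1660. With T = 4.5 the same row gives 1851.

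| Block (accrual/follow-up) | Printed | T = 4 | T = 4.5 |
|---|---|---|---|
| 90 v 85 (3/3, 3/4, 3/5, 4/4, 4/5) | 1660, 1380, 1190, 1280, 1114 | 1660, 1381, 1188, 1278, 1114 | 1851, 1537, 1320, 1421, 1236 |
| 92 v 85 (3/3, 3/4, 4/4, 4/5) | 794, 660, 612, 532 | 793, 659, 610, 531 | 885, 734, 679, 590 |

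The 3/5 row of the 92 v 85 block is not legible and is left out. All nine legible rows match within 2 patients at 4 years. None matches at 4.5 years, where the values are about 11% higher (1851/1660 = 1.115).

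**Step 2: the middle block.** The lower rate reads as 84. At T = 4 with 84, no row matches (for example 3/4 gives 995 against 760). With 83, which is 90 minus the 7% margin, four rows match: 758, 653, 613, 656 against the printed 760, 654, 614, 656. Two do not match under either rate. The 3/3 row (750) gives 910 with 83 and 1195 with 84. The 4.5/4.5 row (740) gives 634 with 83 and 831 with 84.

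**Step 3: where 740 could come from.**
- Comparing 4.5-year proportions, with 90% at 4.5 years and margin 7.2%: N = 4 × 0.9 × 0.1 × 10.507/0.072² = 730.
- The table's formula with 90% at 4.5 years and 7.2%: 669.
- The table's formula with 90% at 4 years and a 7.2% margin at 4.5 years: 718.

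Both 730 and 718 are within about 3% of 740, so the row does not reveal its own method.

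**Step 4: equivalence power at N = 740 under each reading.** Power = 2Φ(x − 1.96) − 1. For fixed-time proportions, x = margin/√(2p(1−p)/370), with standard error 0.02206 at p = 0.900 and 0.02317 at p = 0.8882. For the table's method, x = √{(740/2)(l1 − l2)²/[l1²/P1 + l2²/P2]}, with both rates read at 4.5 years and A = F = 4.5.

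| Control rate | Margin | Proportions: x, power | Table's method: x, power |
|---|---|---|---|
| 90% at 4.5 y | 7.2% | 3.264, 80.8% | 3.410, 85.3% |
| 90% at 4.5 y | 7% | 3.174, 77.5% | 3.327, 82.8% |
| 90% at 4 y (88.8% at 4.5 y) | 7.2% | 3.108, 74.9% | 3.290, 81.6% |
| 90% at 4 y (88.8% at 4.5 y) | 7% | 3.022, 71.2% | 3.209, 78.8% |

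**Step 5: the pair of stated powers.** With a symmetric margin, true difference zero and the same one-sided level, non-inferiority power is Φ(x − 1.96), so equivalence power = 2 × (non-inferiority power) − 1, whichever method supplies x. Then 80% equivalence implies (1 + 0.80)/2 = 90% non-inferiority, and 87% non-inferiority implies 2 × 0.87 − 1 = 74% equivalence. A looser non-inferiority level would push the figure above 90%, further from 87%.

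**The case against.** The best defence is that this is a label error and the chosen design is sound. The 740 row is not one of the rows that follow 4-year arithmetic. A comparison of proportions with 90% at 4.5 years and a 7.2% margin gives 730 and 80.8% power, in line with the text. On that view only the header and section 5.2 are off. This stands as a possible reading, but the protocol does not state it. It also leaves a table whose legible rows belong to a different time point from the one the text announces.

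A reader might go further and infer that 740 patients give about 75% power and not 80%. The documents do not support that as a single figure. The 75% needs both the 4-year rate and a fixed-time comparison of proportions, a method that the protocol does not name. Section 9.0 speaks of exponential survival times, and section 10.2 makes the log-rank test the primary comparison. By the table's own formula the 4-year reading gives 81.6% at 7.2%.

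A reader might also take the 87% as proof of an 88.8% control rate, because that rate gives 87.5% by proportions at 7.2%. Other inputs do as well. With 90% at 4.5 years, an assumed 10% loss (333 per arm) gives 87.2%, and a 6.8% margin gives 86.9%. The inputs behind 87% are not stated, so it identifies nothing.

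The mismatch of the two powers rests on a true difference of zero, the usual convention. An assumed small deficit for the new operation could reconcile them. At 90% and 7.2%, a deficit of 0.39 points (0.0039/0.02206 = 0.177) gives non-inferiority power Φ(3.264 − 0.177 − 1.96) = 87.0% and equivalence power 0.870 − Φ(−(3.264 + 0.177 − 1.96)) = 80.1%. Section 9.0 states no such assumption.

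**Conclusion.** The inconsistency is real. One 90% control rate carries two time points, and the legible rows of two table blocks are 4-year figures although the text presents them as 4.5-year figures. Read at 4.5 years they are about 11% too small. Four of the six middle-block rows show the same pattern, but only if 84 is read as 83. The 750 and 740 rows fit neither 83 nor 84 at 4 years.

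With a true difference of zero, 80% equivalence power and 87% non-inferiority power are incompatible at one N, margin and one-sided 2.5% level.

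The effect on power is a range. If 90% is the 4-year rate, equivalence power at 740 is about 75% to 82% at a 7.2% margin and 71% to 79% at 7%. If it is the 4.5-year rate, the ranges are 81% to 85% and 78% to 83%. A shortfall from 80% at 7.2% is not established. At 7% with the 4-year rate, power is below 80% by both methods. These figures assume exponential survival, uniform accrual and no losses.

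**What to change.** - Use one time point for the 90% in section 5.2, the section 9.0 text and the table header.
- If 90% is the 4.5-year rate, recompute the whole table at 4.5 years, including the 750 and 740 rows, and correct section 5.2 and the header. If it is the 4-year rate, label the table as 4-year, check the 750 and 740 rows, and give the expected 4.5-year rate as 88.8%.
- Correct or confirm the middle-block rate (84 or 83).
- State the method, margin (7% or 7.2%), assumed true difference and other inputs behind 740.
- Restate equivalence and non-inferiority power as a coherent pair from that one method.

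The cost is wording and recalculation in sections 5.2 and 9.0, with no change in enrolment. The downside is a possibly less favourable stated power or larger table entries.

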12.4 FOLLOW-UP VISITS

Follow-up visits begin at 9 months following surgery and continue every 3 months thereafter for the first 2 years and every 6 months until year 4.5.

Follow Up eCRF Visits (not including QoL questionnaires) can be collected using the following time frames:

| Time point | Patient Disease Status Data can be gathered (not including QoL) |
|------------|----------------------------------------------------------------------------------------------------------|
| Visit 1 PO | 3 days either side of due date of Week 1 |
| Visit 2 PO | 1 week either side of due date of Week 6 |
| Visit 3 PO | 2 weeks either side of due date of Month 3 |
| Visit 4 PO | 1 month either side of due date of Month 6 |
| FU 1 | Anytime between date of Month 6 visit and 2 weeks after due date of 9 Months post op |
| FU 2 | Anytime between date of Month 9 visit and 2 weeks after due date of 12 Months post op |
| FU 3 | Anytime between date of Month 12 visit and 2 weeks after due date of 15 Months post op |
| FU 4 | Anytime between date of Month 15 visit and 2 weeks after due date of 18 Months post op |
| FU 5 | Anytime between date of Month 18 visit and 2 weeks after due date of 21 Months post op |
| FU 6 | Anytime between date of Month 21 visit and 2 weeks after due date of 24 Months post op |
| FU 7 | Anytime between date of Month 24 visit and 2 weeks after due date of 30 Months post op |
| FU 8 | Anytime between date of Month 30 visit and 2 weeks after due date of 36 Months post op |
| FU 9 | Anytime between date of Month 36 visit and 2 weeks after due date of 42 Months post op |
| FU 10 | Anytime between date of Month 42 visit and 2 weeks after due date of 48 Months post op |
| | As close to Month 54 as possible (can be a month either side) to accurately assess disease free survival |
| FU 11 | following 4.5 years post op. |

The following procedures will be performed at follow-up visits if data available (if no data available for a FU visit, this is not considered a deviation of Protocol unless it is continual):

- A Clinical assessment including an internal examination will be performed from visit 5 (3 months postoperatively)
- Histological and/or Radiological confirmation of recurrent disease will be obtained to prove the
 presence of recurrent disease. The date of recurrence, its localization and its subsequent
 treatment will be recorded.

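### Section 9.0 gives two equivalence margins (7% and 7.2%), its table does not yield N=740, the time point is 4 or 4.5 years, and the two power figures do not pair.

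*Protocol*

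**What the plan says.** All of this is in Protocol section 9.0 unless stated.

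- Decision rule, first paragraph: "If the disease free survival does not differ by more than 7% then the two procedures will be considered to be equivalent".
- Control rate, second paragraph: "The 4.5 year disease free survival rate for patients undergoing TARH is estimated to be 90"%. Survival times are taken as exponential. "The sample sizes assume a power of 80%, 95% confidence and two-tailed comparisons".
- Sample size, third paragraph: citing the table, 740 patients (370 per arm), with 4.5 years of accrual and 4.5 of follow-up, "would be sufficient to declare equivalence with an equivalence margin of 7.2% or less at 4.5 years".
- Non-inferiority: "This sample size will have 87% power to detect a non-inferiority margin of the same magnitude".
- Table header: "4yr Disease Free Survival difference to be regarded as equivalent".
- Table, block printed as 84 vs 90 (accrual + follow-up in years): 3+3: 750; 3+4: 760; 3+5: 654; 4.5+4.5: 740; 4+5: 614; 5+4: 656.

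Two other sections bear on this. Section 5.2, in describing the single-cohort option, calls the same 90% a four-year rate. Section 12.4 schedules visits "every 6 months until year 4.5".

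**The concern.** The margin is the success criterion for the primary endpoint, and it is given two values. The difference is only 0.2 points, but if it is settled after outcome data are seen, the choice can look driven by the result.

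The sample size is said to rest on the table, so the table should yield it. Some faults show without calculation. A further year of follow-up cannot raise the number needed from 750 to 760. And 740 for 4.5+4.5 years lies well above both 614 for 4+5 and 656 for 5+4, each of which also runs nine years in total. If 740 came from somewhere else, the reader cannot tell what power the trial has, at which margin, or for which year's survival rate.

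**Working it through.** **Inputs.** From section 9.0: control rate 90%; margins 7 and 7.2 points; 370 per arm; 80% power; 95% confidence; exponential survival. From section 12.4: visits end at 4.5 years. Assumptions: uniform accrual; no loss to follow-up (section 9.0 states no allowance); 0.025 on each side for equivalence.

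**1. Reproducing the table.** For equivalence with equal true rates, 80% power uses z = 1.960 + 1.2816 = 3.2415. Freedman's formula with rates fixed at 4 years is:

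- events d = z² × [(h+1)/(h−1)]², with h = ln S₁ / ln S₂
- probability of an event p = 1 − [e^(−λF) − e^(−λ(A+F))]/(λA), with λ = −ln S / 4, A accrual, F follow-up
- N = 2d / (p₁ + p₂)

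| Block | Printed | Computed |
|---|---|---|
| 85 vs 90 | 1660, 1380, 1190, 1280, 1114 | 1660, 1380, 1187, 1278, 1113 |
| 85 vs 92 (legible entries) | 794, 660, 612, 532 | 793, 659, 610, 531 |

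So this is evidently the table's method.

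**2. The block printed as 84 vs 90.**

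| Accrual + follow-up | Printed | Computed, 84 vs 90 | Computed, 83 vs 90 |
|---|---|---|---|
| 3+3 | 750 | 1195 | 909 |
| 3+4 | 760 | 995 | 758 |
| 3+5 | 654 | 856 | 653 |
| 4.5+4.5 | 740 | 830 | 633 |
| 4+5 | 614 | 803 | 613 |
| 5+4 | 656 | 859 | 655 |

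No entry fits 84 vs 90. Four of six fit 83 vs 90, a 7-point difference. The entries 750 and 740 fit neither.

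For 83 vs 90: h = ln 0.83 / ln 0.90 = 1.7685, and d = 3.2415² × (2.7685/0.7685)² = 136.4. At 4.5+4.5 years, p₁ + p₂ = 0.2685 + 0.1624 = 0.4309, so N = 272.8/0.4309 ≈ 633. At 3+3 years, p₁ + p₂ = 0.1884 + 0.1115 = 0.3000, so N ≈ 909.

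**3. Time point.** If 90% and 83% are 4.5-year rates, as the text has it, the hazards fall. The same formula then gives about 702 at 4.5+4.5 and about 1013 at 3+3. Every table entry would change, so 909 is the corrected 3+3 figure only if 4 years is meant.

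**4. Power of 740 on fixed 4.5-year proportions.** With 90% in both arms, SE = √(2 × 0.9 × 0.1 / 370) = 0.02206. Non-inferiority power = Φ(m/SE − 1.96); equivalence power = 2Φ(m/SE − 1.96) − 1.

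| Margin | m/SE − 1.96 | Non-inferiority | Equivalence |
|---|---|---|---|
| 7.2 points | 1.304 | 90.4% | 80.8% |
| 7 points | 1.214 | 88.8% | 77.5% |

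The margin giving exactly 80% is 3.2415 × 0.02206 = 7.15 points. For 80% power the required N is about 730 at 7.2 points and 772 at 7.

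**5. Power of 740 at 7 points by the table's formula,** with follow-up credited to study end: z = 3.2415 × √(740/N).

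- 4.5-year hazards, N = 702: z = 3.328; Φ(1.368) = 0.914; equivalence power about 83%.
- 4-year hazards, N = 633: z = 3.505; Φ(1.545) = 0.939; equivalence power about 88%.

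**6. The 80% and 87% pair.** With equal true rates and the same method and alpha, equivalence power = 2 × non-inferiority power − 1. Then 80% pairs with 90%, and 87% pairs with 2 × 0.87 − 1 = 74%.

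**The case against.** **Only one sentence is a decision rule, and it says 7%.** True. The 7.2% stands in a sample-size statement and may be the 7.15 points of step 4 rounded up. A reader might infer that a confidence limit of 7.1 points would pass one sentence and fail the other, but section 9.0 states no confidence-limit rule. What stands is that section 9.0 calls both figures the level for declaring equivalence.

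**740 is not underpowered at 7 points.** A reader might infer that 740 reaches 80% only at 7.2 points. The protocol does not support that. It names exponential survival, and by the table's formula 740 exceeds 80% at 7 points. The shortfall to 77.5% appears on fixed proportions, a method the protocol never names. In turn, the table's formula credits follow-up to study end, up to nine years for the first entrants, while scheduled visits end at 4.5 years. Neither figure can be taken as the trial's power until the method is stated.

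**The 6-point label may be a typographical or reading error.** This stands. A reader might infer a third margin of 6 points from the label 84, but the legibility of that label is doubtful and four of the block's six numbers are those of 83 vs 90. It is a mismatch between label and numbers. Likewise, the 3+5 entry under 85 vs 92 is broken in the text available and is not counted as an error.

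**80% and 87% could come from different methods.** Possible, since no method is given for the 87%. The pair is therefore unexplained, not proven impossible. It cannot come from one method with equal true rates, a symmetric margin and one alpha.

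**Conclusion.** The point holds. Section 9.0 gives two margins; "or less" reverses the relation between margin and sample size; the table's evident method does not yield 740 (about 633) or 750 (about 909); the 90% is tied to both 4 and 4.5 years; and the two power figures do not pair under one method.

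The effect on power is modest. On fixed 4.5-year proportions, which match the visit schedule, moving from 7.2 to 7 points lowers equivalence power from 80.8% to 77.5% and non-inferiority power from 90.4% to 88.8%. By the table's formula, equivalence power at 7 points is about 83% or 88%, depending on the year to which the rates refer. These figures assume 90% in both arms, 0.025 per side and no loss. They do not show that the trial is too small. They show that its margin and power cannot be read from the protocol as written.

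**What to change.** 1. Use one margin throughout: 7 points, the stated decision rule. Replace 7.2% and delete "or less".
2. State whether the 90% is a 4-year or 4.5-year rate, align section 5.2 with it, and recompute the whole table at that time point. Check the label 84 against the source calculation and correct the 3+3 and 4.5+4.5 entries.
3. State the method and assumptions behind 740, including whether follow-up beyond 4.5 years is counted. If 740 was not derived from the table, take it out and remove the statement that it rests on those numbers.
4. Restate equivalence and non-inferiority power at 7 points from that one method. If it is fixed 4.5-year proportions, these are about 77% and 89%.

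The cost is wording and one recalculation, with no additional patients. The stated power may become slightly less favourable.

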10.0 STATISTICAL ANALYSES

Primary endpoints will be analyzed according to the intention-to-treat principle. However, as this is a non-inferiority design, there is a view by some biostatisticians that, if there are patients who do not receive the allocated treatment (and in fact 'cross-over' to the alternate arm) an analysis by intention to treat will bias the analysis in favour of the alternate hypothesis that the two groups are not inferior. To overcome this issue, a 'per protocol' analysis i.e. only include those patients who were treated according to the protocol would be used. Therefore being a "modified" version of intent to treat analysis as conveyed to the Trial Safety Committee on 1st October 2014.

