7.0 OUTCOMES

7.1 PRIMARY OUTCOME MEASURES

Treatment equivalence as evaluated by: Disease-free survival at 4.5 years post-surgery, as measured by the time interval between date of surgery and date of first recurrence. Histological confirmation of recurrent disease will prove the presence of recurrent disease.

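### The primary hypothesis is equivalence in sections 5.0, 7.1 and 9.0 but non-inferiority in 10.0; the two rules part when TLRH/TRRH looks better, and the 80% and 87% powers do not fit together

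*Protocol*

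**What the plan says.** All references are to the protocol.

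- **Equivalence.** Section 5.0 calls the trial an equivalence study. Section 7.1 heads the primary outcome "Treatment equivalence as evaluated by: Disease-free survival at 4.5 years post-surgery". Section 9.0 gives the only written decision rule: "If the disease free survival does not differ by more than 7% then the two procedures will be considered to be equivalent". It adds "The sample sizes assume a power of 80%, 95% confidence and two-tailed comparisons" and says 370 per arm is enough for an equivalence claim at a margin of 7.2% or less.
- **Non-inferiority.** Section 10.0 says "as this is a non-inferiority design, there is a view by some biostatisticians that" intention-to-treat can bias the result, and on that ground brings in a per-protocol analysis. So the label has a consequence for the analysis.
- **Mixed wording.** Option 1 in section 5.2 speaks of "determining whether TLRH is at least equivalent to TARH", which points in one direction only. Section 9.0 ends its sample-size text with "This sample size will have 87% power to detect a non-inferiority margin of the same magnitude" and gives no alpha for that figure.
- **The named test.** Section 10.2 makes the logrank test the primary comparison and promises 95% confidence intervals for differences. It ties neither to a margin and does not say whether one or both limits must clear it.

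**The concern.** Equivalence requires both limits of the confidence interval to lie inside the margin. Non-inferiority requires only the limit on the unfavourable side. A trial in which the minimally invasive arm does clearly better can therefore fail the rule in section 9.0 and pass the one implied by section 10.0. This goes beyond detail that could be left to a statistical analysis plan, because a plan written from this protocol would have to contradict one section or another. The two power figures raise a second doubt: they should follow from one calculation, and they do not appear to.

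**Working it through.** **Inputs.** Section 9.0: 370 per arm, TARH 4.5-year DFS 90%, margin 7.2 points for the sample size and 7% in the rule, 95% confidence, 80% power, exponential survival. Assumed here: no true difference under the planning alternative, and complete follow-up for the calculations on proportions.

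**1. The plan's own figure, on proportions.** With no true difference, 80% equivalence power leaves 10% error on each side, so z = 1.2816. At 2.5% per side:

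n per arm = (1.96 + 1.2816)² × 2 × 0.9 × 0.1 / 0.072² = 10.508 × 0.18 / 0.005184 = 364.9, so 365 per arm and 730 in total, against 740 stated.

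**2. Power at 370 per arm.** SE = √(2 × 0.9 × 0.1 / 370) = 0.02206.

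- 7.2 points: 0.072 / SE = 3.264. Non-inferiority Φ(3.264 − 1.96) = 90.4%. Equivalence 2 × 0.904 − 1 = 80.8%.
- 7 points: 0.070 / SE = 3.174. Non-inferiority Φ(3.174 − 1.96) = 88.8%. Equivalence 77.5%.

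**3. Do 80% and 87% fit together?** With one alpha, one symmetric margin and no true difference, equivalence power = 2 × non-inferiority power − 1. So 80% implies (0.80 + 1) / 2 = 90%, and 87% implies 2 × 0.87 − 1 = 74%.

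**4. The same check on the exponential model.** N = 2(z_a + z_b)² (λ₀²/p₀ + λ₁²/p₁) / (λ₁ − λ₀)², where λ = −ln(DFS)/T and p is the expected event proportion for the given accrual and follow-up. With z_a = 1.96, z_b = 1.2816 and T = 4 years, the 85 v 90 block gives 1660, 1381, 1188, 1278 and 1114, against the table's 1660, 1380, 1190, 1280 and 1114. For 4.5 + 4.5 years it does not give 740. Non-inferiority power at 740 is Φ(3.2416 × √(740/N) − 1.96):

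| Rates | N for 80% equivalence | Non-inferiority power at 740 | Equivalence power at 740 |
|---|---|---|---|
| 84 v 90, 4-year | 831 | 86.4% | 72.8% |
| 83 v 90, 4-year | 634 | 93.9% | 87.7% |
| 84 v 90, 4.5-year | 922 | 82.7% | 65.5% |
| 83 v 90, 4.5-year | 703 | 91.4% | 82.8% |

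No row pairs 80% with 87%.

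**5. Verdict on one result.** Observed 94% v 90%: SE = √((0.94 × 0.06 + 0.90 × 0.10) / 370) = 0.01989. The difference is +4.0 points, 95% CI 4.0 ± 1.96 × 1.989 = +0.1 to +7.9. The lower limit clears the margin and the upper limit does not, at 7 or at 7.2 points.

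**6. How often the rules disagree** (non-inferiority power minus equivalence power, normal approximation, TARH 90%):

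| True TLRH/TRRH | 7.2-point margin | 7-point margin |
|---|---|---|
| 90% | 90.4 − 80.8 = about 10% | 88.8 − 77.5 = about 11% |
| 92% | 99.2 − 68.8 = about 30% | 99.0 − 65.2 = about 34% |
| 93% | 99.9 − 53.5 = about 46% | 99.8 − 49.6 = about 50% |
| 94% | 100 − 36.3 = about 64% | 100 − 32.6 = about 67% |

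**The case against.** **Only one decision rule is written.** Section 9.0 holds it. Section 10.0 uses the non-inferiority label in passing, and the 87% sentence is a supplementary power statement. A reader might infer that section 10.0 prescribes a one-sided test. It does not: no one-sided level appears anywhere, and the only explicit statement of sidedness is two-tailed. This stands. The conflict is between labels and what they imply, not between two written tests.

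**The consequence is limited to one side.** At equal margin and alpha, passing equivalence implies passing non-inferiority, so the rules part only when the new arm looks better. A reader might infer that a worse operation could pass one rule and fail the other. That would need a looser alpha for non-inferiority. At one-sided 5%, an observed 87% v 90% has a lower limit of −6.85 and would pass at 7.2 points, while its 95% CI of −7.6 to +1.6 fails equivalence. Nothing in the protocol sets that level. The larger disagreement rates also assume true gains of 2 to 4 points, which the protocol does not anticipate; its background expects similar outcomes.

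**The 87% cannot be corrected from the document alone.** A reader might infer that it should be 90%, or that it implies an alpha near 1.6% (3.264 − 1.126 = 2.138, upper tail 0.016). Both rest on proportions with complete follow-up, whereas section 9.0 states exponential survival. On that model, figures on either side of 87% arise at the ordinary 2.5% level, including 86.4% for the rates in the table row that holds 740. What survives is narrower: the two powers do not belong to one calculation, and the alpha of the second is missing.

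**Conclusion.** The concern holds in this form. The protocol names its primary hypothesis in two ways, and the difference changes the conclusion for results that favour TLRH/TRRH. Under the planning assumption of no true difference, about 10% of trials would be non-inferior but not equivalent. This rests on 370 per arm, 90% DFS, a two-sided 95% CI, a 7.2-point margin and complete follow-up. The 80% and 87% are incompatible under one alpha, one symmetric margin and one model with no true difference; which of them is off cannot be settled without knowing the model and alpha behind each. The logrank test named in section 10.2 does not help, because it tests for no difference and so implements neither rule. The protocol does not show that a worse operation could be accepted, or that the choice of rule would be made after seeing results; a statistical analysis plan may exist.

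**What to change.** State one decision rule, in the same words, in sections 5.0, 7.1, 9.0 and 10. Base it on the two-sided 95% CI for the 4.5-year DFS difference (TLRH/TRRH minus TARH) and one named margin, which means reconciling 7% with 7.2%. Let this rule, not the logrank test, decide the primary claim. One workable form is:

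1. Declare non-inferiority if the lower limit is above minus the margin.
2. If so, declare equivalence from the same interval if the upper limit is also below plus the margin. Equivalence is nested in non-inferiority, so no alpha is spent.

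Keeping equivalence alone as the primary claim would also be consistent, provided section 10.0 and the *at least equivalent* wording in 5.2 are changed to match.

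Recompute and restate both powers from one stated model, margin and alpha. On proportions of 90% with complete follow-up and 2.5% per side, 740 patients give about 90% (non-inferiority) and 81% (equivalence) at 7.2 points, and about 89% and 78% at 7 points. The 90% should not be inserted without that basis.

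The cost is wording and restated power figures, with no extra patients. If 7 points is chosen, the stated equivalence power falls slightly below 80%.
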